Study Protocol and Statistical Analysis Plan

Clinicaltrials.gov ID: NCT05178979

Unique Protocol ID: K01MH121663-01A1

Secondary IDs: 1K01MH121663-01A1 [U.S. NIH Grant/Contract Award Number]

Title: A Gender Transformative Implementation Strategy With Providers to

Improve HIV Outcomes in Uganda

Protocol date: 11 July 2023 (final version date of approved IRB protocol)

Pls: [name]

Contact PI: [name], BC, [contact]

Contents

Inclusion criteria	3
Recruitment & Sampling	3
Data collection	4
Questionnaires	4
Process Data	5
Data management	6
Qualitative data	6
Quantitative data	6
Data safety monitoring plan	7
Adverse events	7
Training of the RAs/Facilitators	8
Training of research assistants	8
Training of intervention facilitators	8
Statistical Analysis Plan	9

Inclusion criteria

Provider cohort for training intervention, assessment, and exit focus groups (intervention trial). We will recruit providers for participation in our intervention trial for the provider training from the two selected clinics. The goal is to recruit the entire population of providers at each of the two clinics, which is approximately 20-35 providers per clinic (Luwero Hospital, Mityana Hospital, Kalagala HCIV and Namayumba HCIV) for participation. This cohort will include all HIV care providers at the 4 selected clinics, including: medical officers, clinical officers, HIV nurses, midwife, linkage facilitators, and counselors. These participants will be 18 years of age or older and fluent in English or Luganda.

Patient cohort assessment (intervention trial). In addition to the assessment of the cohort of ~80-140 HIV providers, we will obtain additional data on the impact of the provider training on patient outcomes including quality of care, patient satisfaction, clinic attendance, ART adherence, and viral load (from patient clinic records) by assessing 240 (60 per treatment facility, gender balanced) purposively sampled patients at baseline, 6-, and 12-month follow-up.

Eligibility includes:

- 1. HIV-infected;
- 2. enrolled in care at the clinic of recruitment;
- 3. pre-ART (newly diagnosed) or newly initiated on ART (within 1 year) or struggling with treatment adherence, defined in two ways:
 - a. most recent viral load results unsuppressed as assessed through clinic records

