 - or self-reported non-adherence as by the Adult AIDS Clinical Trials Group (AACTG) scale 4-day adherence recall questions. This scale has demonstrated good construct validity in Uganda and strong correlations with viral load;
- 4. 18 years of age or an emancipated minor;
- 5. fluent in Luganda or English.

Recruitment & Sampling

Provider cohort for training intervention, assessment, and exit focus groups (intervention trial). Once research staff are trained and our two clinics have been randomly assigned as intervention or control arm, we will recruit providers for participation in our intervention trial for the provider training. The goal is to recruit the entire population of providers at each of the four clinics, which is approximately 20-35 providers per clinic (Luwero Hospital, Mityana Hospital, Kalagala HCIV, and Namayumba HCIV) for participation; approximately 35 at each hospital and 25 at each HCIV (total: 80-140). With support from Mildmay Uganda (see Letter of Support), we will generate support for the training first in the broader Health Districts (with medical superintendents and District Health Officers) through in-person meetings and garnering their feedback on the intervention through invitations to serve on/make recommendations for a "Training Steering Committee." After District support is attained, we will then conduct facility mobilization with an inperson presentation of the goals research study at each of the four clinics. Eligibility for providers includes being an HIV care provider at one of the four selected clinics. After the larger facility

mobilization meeting, the research assistant will meet one-on-one with HIV providers to individually inform them of the study, allow them to ask any questions in a private space, and obtain written informed consent. Though we aim to recruit all HIV providers at each clinic for participation, any provider can decline to participate. The informed consent process will include consent for both participation in the provider training, baseline, 6- and 12-month assessments, and an exit focus group. To mask the randomization of intervention and control, we will consent participants for participation in all aspects of the training.

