Patient cohort assessment (intervention trial). In addition to the assessment of the cohort of ~140 HIV providers, we will obtain additional data on the impact of the provider training on patient outcomes including quality of care, patient satisfaction, clinic attendance, ART adherence, and viral load (from patient clinic records) by assessing 240 (60 per clinic, gender balanced) purposively sampled patients at baseline, 6- and 12-month follow-up. Patients will be non-randomly approached when presenting to care by a Research Assistant based on a review of clinic records. After being referred by a clinician, our research assistant will inform individuals of the study and assess eligibility using an eligibility screening tool. No identifying information will be recorded during the eligibility screening. If eligibility is met and the patient would like to participate, the research assistant will obtain written informed consent and collect patients' contact information (for follow-up reminders) and conduct the baseline questionnaire in the clinic or another agreed upon location.

Data collection Questionnaires

For the provider cohorts randomized to the Intervention clinics, the chronological activities include: enrollment; baseline interview immediately after enrollment; participation in ~21 hours of intervention content; follow-up assessments at 6-months and 12-months follow-up; one exit focus group post-intervention. Each data collection activity and its duration is detailed below:

- Baseline provider assessment (for all provider participants). After the informed consent process a one-on-one interview (~25 minutes) using a computerized structured questionnaire in the clinic or another agreed upon location will be conducted with providers at both clinics. The questionnaire will collect demographic information and measures to assess provider outcomes. The total duration of participation for the baseline survey is approximately 25 minutes.

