To evaluate the time by intervention effect on primary and secondary outcomes, we used Generalized Estimating Equations (GEE) in SPSS v. 28, which can account for dependency in the data related to the clinic clusters and repeated measures. First, we used GEE to examine baseline equivalence between treatment arms in both HIV care provider and client cohorts. We tested variables that differed at a level of p < 0.10 between treatment arms as covariates in the models testing intervention effect; only variables significant at p < 0.05 and/or making a difference in the intervention effect were maintained in the final models. We report the time by arm interaction. For all provider and client analyses, we tested the time by intervention by gender effect. For providers, we also tested the time by intervention by cadre effect, categorizing providers into certified health workers (licensed doctors, nurses, counselors) vs. lay health workers or non-specialized staff (e.g., peers). These interactions are only presented if they were statistically significant (p < 0.05). We report unstandardized betas (b) and standard errors (SE) for continuous outcomes and odds ratios (ORs) and adjusted odds ratios (AORs) and 95% confidence intervals (CIs) for binary outcomes.

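### The SAP relies on GEE to handle clustering by clinic with four named clinics, but states no GEE subject, variance estimator, degrees of freedom or few-cluster correction, and no usual uncorrected choice is reliably valid with so few clusters.

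*Combined protocol and SAP*

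**What the plan says.** Allocation is by clinic. Recruitment & Sampling says "our two clinics have been randomly assigned as intervention or control arm", and Data collection says "For the provider cohorts randomized to the Intervention clinics". The number of clinics is inconsistent. The wording just quoted from Recruitment & Sampling says two, while Inclusion criteria says "This cohort will include all HIV care providers at the 4 selected clinics" and names two hospitals and two HCIVs. The split between arms is not stated.

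Patient numbers are given as "assessing 240 (60 per treatment facility, gender balanced) purposively sampled patients". Provider numbers are put at 20 to 35 per clinic, and also as "approximately 35 at each hospital and 25 at each HCIV".

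The Statistical Analysis Plan is one paragraph in the past tense. On clustering it says only that GEE in SPSS v. 28 was used, "which can account for dependency in the data related to the clinic clusters and repeated measures". The time-by-arm interaction is the reported effect. For its precision the plan says "We report unstandardized betas (b) and standard errors (SE) for continuous outcomes", with odds ratios and 95% confidence intervals for binary outcomes. On gender and cadre it says "These interactions are only presented if they were statistically significant (p < 0.05".

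**The concern.** Saying that GEE can account for clinic clustering describes what the method is able to do. It does not say what was fitted. The user must choose the subject, the working correlation and the variance estimator, and the usual justification for robust GEE standard errors needs many independent clusters. Here there are at most four.

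If the standard errors are too small, ordinary drift between clinics over 12 months can be read as an effect of the training, for providers and patients alike. The same standard errors drive the p < 0.05 rule that decides which gender and cadre interactions are shown.

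**Working it through.** **The plan's own figures.** 4 × 60 = 240 matches the patient total; two clinics would give 120. For providers, 4 × 20 = 80 and 4 × 35 = 140 match the stated range, and 2 × 35 + 2 × 25 = 120 lies inside it. So the sample sizes fit four clinics. The documents give no power calculation, SD or ICC to reproduce.

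**Assumptions.** Two clinics per arm; two-sided 5%; for providers with 35 and 25 per clinic, one hospital and one HCIV in each arm. ICC means the clinic ICC of the change score, taken as 0 to 0.05. A stable difference between clinics cancels in time-by-arm, so only clinic-by-time variation counts.

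**(1) Clinic as subject, uncorrected robust variance, normal reference.** The contrast compares two clinic mean changes with two others. In an arm with two clinics, the sandwich divides the sum of squared residuals by 4, where the unbiased variance of the mean divides it by 2. The estimated variance is therefore half of the unbiased one, and the test rejects when |t on 2 df| > 1.96/√2 = 1.386. The tail is 1 − 1.386/√(2 + 1.921) = 0.300, and the ICC does not enter. GEE fits to simulated data (400 per setting) gave 0.295 to 0.315 for continuous and 0.285 to 0.315 for binary outcomes.

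**(2) Participant as subject.** Clinic-by-time variation is ignored. Type I error = 2(1 − Φ(1.96/√DEFF)). DEFF is 1 + 59 × ICC for patients, 1 + 19 × ICC for 20 providers per clinic, and 1 + 29.83 × ICC for 35 and 25, since (35² + 25²)/60 − 1 = 29.83.

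**(3) Clinic as subject, model-based SEs, exchangeable correlation.** This misses the within-participant correlation, assumed to be 0.5. Type I error = 2(1 − Φ(1.96/√(0.5 × DEFF))). It crosses 5% at ICC = 1/59 = 0.017 for patients.

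| ICC of change | 0 | 0.005 | 0.01 | 0.02 | 0.05 |
|---|---|---|---|---|---|
| (1) clinic, robust | 30% | 30% | 30% | 30% | 30% |
| (2) patients, 60 per clinic | 5.0% | 8.5% | 12.0% | 18.4% | 32.4% |
| (2) providers, 20 per clinic | 5.0% | 6.1% | 7.2% | 9.5% | 16.0% |
| (2) providers, 35 and 25 | 5.0% | 6.7% | 8.5% | 12.1% | 21.4% |
| (3) patients, model-based | 0.6% | 1.5% | 2.8% | 6.0% | 16.3% |

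**Gender interaction, patients.** Under (1) each clinic again contributes one number, so the rate stays near 30% (simulation: 29.6% to 30.4%). Under (2) a clinic-by-time effect shared by men and women cancels (4.6% to 5.5%). Inflation needs clinics to differ in gender-specific change.

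**A clinic-level alternative.** Comparing the clinics' mean changes with t on 2 df (critical value 4.303) holds 5% when clinic changes are near normal with similar variance in both arms. With a 2:2 split each clinic has leverage 1/2, so the Kauermann-Carroll correction doubles the robust variance and, with t on 2 df, also gives 5%. If one arm's clinic variance is 9 times the other's, size is about 0.075, with a limit near 0.145.

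**Width of that interval, patients.** The SE is itself estimated on 2 df, with mean 0.886 of its true value.
- ICC 0: mean width ratio to participant-clustered GEE is 4.303 × 0.886/1.96 ≈ 1.9. Mean half-width is 4.303 × 0.886 × √(1/60) ≈ 0.49 SD of change, against 1.96 × √(1/60) ≈ 0.25.
- ICC 0.02: multiply by √2.18, giving about 2.9 times and 0.73 SD.
- The 2-df interval comes out narrower in 1 − exp(−(1.96/4.303)²) ≈ 19% of data sets at ICC 0, and about 9% at ICC 0.02.

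**The case against.** The strongest reply is that only non-disclosure is certain. The type I error in the table runs from 0.6% to 32.4% according to choices and an ICC that nobody outside the team knows. With participant as subject and no clinic-by-time variation the analysis is sound. That stands: a reader might infer that the reported effects carry a 30% false-positive rate, and the documents do not support it. They do not show that this model was run, and they contain no results.

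A second reply is that the 2-df test is fragile too. It needs an equal-variance assumption that four clinics cannot verify, its intervals vary greatly in width, and an effect with 80% power under a normal reference has about 35%. This also stands. It is a reason to report the clinic-level result beside the GEE result and not as an unquestioned replacement.

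Two other readings go too far. One is that no valid analysis exists; clinic-level methods hold their size under stated assumptions. The other is that the split may be lopsided. No text suggests that, and the plural in "For the provider cohorts randomized to the Intervention clinics" also sits badly with one clinic per arm. But the references to two clinics remain and have to be settled.

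**Conclusion.** The point holds, and the plan must be corrected. It is certain that the Statistical Analysis Plan rests its inference on GEE with four named clinics while leaving out every setting that determines validity. Given a 2:2 split, it is also certain that the uncorrected clinic-clustered robust analysis, if used, has a type I error of about 30%. The inflation with participant as subject (12.0% to 32.4% for patients at ICCs of 0.01 to 0.05, and 7.2% to 21.4% for providers across the two cluster-size cases) is conditional on an assumed ICC. Model-based standard errors can err in either direction. The 2:2 split, the ICCs and the within-participant correlation are assumptions. The effect on any published estimate cannot be judged from these documents.

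**What to change.** 1. Reconcile the references to two clinics with the four named, and state the split and any pairing of clinics. If there was one clinic per arm, say that no clinic-level inference is possible.
2. State the GEE subject, working correlation, variance estimator and reference distribution that were used.
3. Add a clinic-level analysis of the existing data. Label it post hoc, since the plan is written after the analysis. Compare each clinic's mean change between arms with t on 2 df or, for a 2:2 split, use clinic-clustered GEE with the Kauermann-Carroll correction and t on 2 df. For binary outcomes use the clinic-level change in log odds or risk.
4. Report this beside the GEE result for time-by-arm and for the gender and cadre interactions, whatever their p-values.
5. Do not present uncorrected clinic-clustered robust standard errors as valid. If participant-clustered ones are kept, show the intervals over a range of ICCs. For patients the multipliers √DEFF are 1.00, 1.14, 1.26, 1.48 and 1.99 at the five ICCs in the table.
6. State that the 2-df t assumes near-normal clinic-level changes with similar variance in both arms, which four clinics cannot verify. Describe p-values and intervals as preliminary or exploratory.

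The cost is some wording and a short re-analysis, with no new data. The price is lower power and intervals that are usually wider and highly variable. No re-analysis can supply the replication that a four-clinic design lacks.

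### Gender and cadre three-way interactions are presented only when p < 0.05, so those shown overstate the true size on average and the rest cannot be interpreted

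*Combined protocol and SAP*

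**What the plan says.** All the relevant text is in the Statistical Analysis Plan section.

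- The time × arm result carries no significance condition: "We report the time by arm interaction".
- Gender: "For all provider and client analyses, we tested the time by intervention by gender effect".
- Cadre: "For providers, we also tested the time by intervention by cadre effect", with certified health workers compared with lay or non-specialised staff.
- Presentation rule for the gender and cadre terms: "These interactions are only presented if they were statistically significant (p < 0.05".
- Scale: "We report unstandardized betas (b) and standard errors (SE) for continuous outcomes", and odds ratios with 95% CIs for binary outcomes.

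The section does not list or count the outcomes. It does not call the interactions exploratory, adjust for the number tested, or provide for the omitted estimates to appear elsewhere.

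**The concern.** The rule selects which results are seen by their p-values. This has two consequences.

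1. **Shown interactions are too large on average.** If the test is a single contrast, an estimate must exceed about 2 standard errors to appear. When the true interaction is smaller than that, only overestimates (or, rarely, wrong-sign estimates) can pass.
2. **Omitted interactions are uninformative.** A reader can infer p ≥ 0.05 but sees neither estimate nor precision. A tight null looks the same as an interval wide enough to include a large difference.

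This matters here because the intervention is gender transformative and the patient sample is gender balanced by design (Inclusion criteria). Whether effects differ by gender is a question readers will ask, and a later meta-analysis could draw only on the significant answers.

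**Working it through.** **Inputs from the documents.** The filter is p < 0.05 (taken as two-sided, since sidedness is not stated). Assessments are at baseline, 6 and 12 months for patients ("purposively sampled patients at baseline, 6- and 12-month follow-up") and providers ("baseline, 6- and 12-month assessments, and an exit focus group"), both under Recruitment & Sampling. The documents state no power, SD, effect size or intraclass correlation, so there is no planned figure to reproduce. Results are therefore shown by assumed power.

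**Step 1: single contrast (1 df).** Let z = estimate/SE follow N(d, 1), where d = true interaction/SE. The term is shown if |z| > c = 1.960. With Φ and φ the normal distribution and density functions:

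- Power: P = [1 − Φ(c − d)] + Φ(−c − d)
- Mean absolute size when shown: E(|z| given shown) = {d[1 − Φ(c − d)] + φ(c − d) − dΦ(−c − d) + φ(c + d)}/P
- Overstatement ratio: E(|z| given shown)/d

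| Power | d | Mean shown, in SE | Ratio to truth | Real interaction left out |
|---|---|---|---|---|
| 10% | 0.652 | 2.42 | 3.71 | 90% |
| 20% | 1.115 | 2.52 | 2.26 | 80% |
| 30% | 1.435 | 2.59 | 1.81 | 70% |
| 50% | 1.960 | 2.76 | 1.41 | 50% |
| 80% | 2.802 | 3.15 | 1.12 | 20% |
| 90% | 3.242 | 3.44 | 1.06 | 10% |

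For example, at 20% power: 2.516/1.115 = 2.26. If the true interaction is zero, a shown estimate averages 2.34 SE in absolute size, against 0.80 SE with no filter.

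**Step 2: time as a category (2 df).** The overall test combines the 6- and 12-month contrasts and the term is shown if the Wald statistic exceeds 5.99. The 2-SE gate on a single contrast no longer applies exactly, so this was simulated (2,000,000 draws). The correlation between contrasts was 0.3, 0.5 or 0.7. The true effect was equal at both visits, half-size at 6 months, or present at 12 months only. Over the nine combinations, the overstatement ratio for the 12-month contrast was:

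| Power | Ratio to truth |
|---|---|
| 10% | 2.9–3.3 |
| 20% | 2.0–2.1 |
| 30% | 1.6–1.7 |
| 50% | 1.3–1.4 |
| 80% | 1.1 |

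**Step 3: which rows are plausible?** As an illustration, assume two equal subgroups, so that the interaction SE is twice the SE of the time × arm effect, and assume 80% power for time × arm (d = 2.802). An interaction as large as the time × arm effect then has d = 2.802/2 = 1.401, power 29% and ratio 1.85. One half as large has d = 0.700, power 11% and ratio 3.47.

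**Step 4: chance findings (a side point).** Recruitment & Sampling names five items: "patient outcomes including quality of care, patient satisfaction, clinic attendance, ART adherence, and viral load (from patient clinic records". Data collection names at least two provider outcomes, gender-equitable attitudes and gender awareness. Taking one analysis per named item, an inference because the SAP gives no list, there are 5 + 2 = 7 gender tests and 2 cadre tests, 9 in all. If all are null, validly tested and independent, the chance of at least one false positive is 1 − 0.95⁹ = 0.37. With correlation 0.3, 0.5 or 0.7 within each cohort-and-moderator block it is 0.35, 0.32 or 0.29 (1,000,000 draws). More outcomes would raise it.

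**The case against.** The strongest defence is that little turns on this. The stated aim is the time × arm effect, which is reported unconditionally. Both the interaction testing and the display rule are disclosed, and no fitted model or main estimate changes. That is correct and limits the weight of the point. Disclosure does not supply the missing estimates or their precision.

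Several technical qualifications also stand:

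- **Power is assumed.** If the interactions were well powered, the overstatement would be slight (1.06 at 90% power). The direction is the same at any power below 100%.
- **The ratio uses absolute values.** At 10% power, 4.5% of shown estimates have the wrong sign. The signed ratio is 3.40 instead of 3.71, and an unfiltered estimate already averages about 1.47 times the truth in absolute size (1.00 signed). From about 30% power upwards the signed and absolute ratios for shown estimates are practically equal.
- **Scale.** For binary outcomes the ratios apply to the log-odds coefficient, not to the odds ratio itself.
- **Standard errors.** The ratios assume a correct SE. With four clinics, a cluster-based GEE standard error may be too small. If it were 60% of its true value (an assumption), the ratio at d = 1.11 would fall from 2.27 to 1.75, while more null interactions would pass the filter.
- **Multiplicity is a separate problem.** The false-positive figures rest on an inferred count and do not establish the filter bias.
- **The SAP is written in the past tense.** A changed sentence alone alters nothing already done. The practical gain is the table.

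**Conclusion.** The concern holds. As written, the rule yields a selected set of gender and cadre interactions that overstate the truth on average, and it withholds the estimate and precision of all the others. The overstatement is about twofold or more at 20% power or less and about 1.1-fold at 80%, assuming an approximately normal, unbiased coefficient with a correct standard error. Its actual size in this trial cannot be fixed from the documents. The filter affects every outcome on which the interactions were tested, primary outcomes included, but does not bias the time × arm result. The change should be made, although the trial's main conclusions do not depend on it.

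**What to change.** Replace the presentation rule in the Statistical Analysis Plan with:

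> All time × arm × gender and time × arm × cadre interactions that were tested are reported with estimates and 95% CIs (for each follow-up contrast if time is categorical), whether or not significant, with the number tested, and are labelled exploratory.

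Put them in one supplementary table. The cost is one sentence and that table, since the SAP says the tests were already run.

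This removes the presentation filter: under the same normal model, the expected signed estimate again equals the true value. It also makes the number of tests visible. It does not reduce chance findings, correct standard errors based on few clusters, or establish that the interactions were prespecified.
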